4.4 Study Termination Criteria

Each subject will be informed that they are free to **PPD**

Monitor, or the Medical Monitor may exercise his or her medical judgment to terminate a subject's participation in the study if it is in the best interest of the subject.

If a subject withdraws from the study during the follow-up period, the Investigator should make every effort to have the subject return to the clinic for the end of study safety evaluations.

Medical Monitoring for this study will be conducted by:

PPD **MD**

PPD and **PPD**

EyePoint Pharmaceuticals, Inc.
[name]

Cell: **PPD**

The Sponsor reserves the right to terminate the study at any time. Every effort should be made to collect all data required by the protocol during or following the subject's Early Termination Visit.

In cases of early termination, every effort should be made to complete the case report forms and report the results as thoroughly as possible. A termination electronic case report form (eCRF) page should be completed for every subject who received study treatment whether or not the subject completed the study. The reason for any early termination from the study should be indicated on this form. The primary reason for a subject's early termination should be selected from the following standard categories:

Adverse Event (AE): Clinical or laboratory events occurred that in the medical judgment of the Investigator for the best interest of the subject are grounds for discontinuation. This includes serious AEs (SAEs) and non-serious AEs regardless of the relationship to study drugs.

Subjects who are withdrawn due to AEs must be followed until there is either:

- Resolution
- Stabilization or severity to the National Cancer Institute's Common Toxicity Criteria for Adverse Events (CTCAE) Grade 1/mild
- Returned to baseline status
- Subject is lost to follow-up
- The event is otherwise explained by the Investigator

Death: The subject died during the study.

Withdrawal of Consent: The subject desired to withdraw from further participation in the study in the absence of a medical need to withdraw as determined by the Investigator. If the subject gave a reason for this desire, this should be recorded.

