## 4. Study Details/Design

### 4.1. Brief Description

[figure not shown]
This is a prospective, randomized, double-masked, multicenter study evaluating the ocular efficacy and safety of 2 different doses of the EYP-1901 IVT insert compared to sham in adult subjects with NPDR. Approximately 60 subjects will be randomized in a 1:1:1 ratio to each of three treatment arms (2060 µg EYP-1901, 3090 µg EYP-1901, or sham IVT injection) across approximately 30 sites in the United States, such that each treatment arm will include approximately 20 subjects.

All subjects, irrespective of treatment arm, will receive an IVT injection on Day 1 in the designated study eye. Subjects in the EYP-1901 treatment arms will receive study treatment which is expected to deliver vorolanib into the vitreous humor for at least 9 months, while subjects in the sham treatment arm will receive a sham injection to maintain masking. Following study drug IVT injection on Day 1, subjects will return at Weeks 4, 12, 24, 36 and 48.

For subjects with unilateral NPDR, the affected eye will be designated as the study eye; for subjects with bilateral NPDR, the study eye will be the more severely affected eye meeting the inclusion/exclusion criteria, ie, the eye having the worse Diabetic Retinopathy Severity Scale (DRSS) score or if equal, the eye clinically judged to be the more severely affected eye as determined by the Investigator. If the eyes are symmetrically affected, the study eye will be the right eye. The fellow eye will receive treatment as needed and according to the Investigator's judgment.

The study design including treatment and visit schedules is shown in [Figure 1](#).

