**Footnotes for Table 1:**

- a. Subjects who terminate the study prior to the Week 48 (end of study) visit should undergo all procedures noted for the early termination visit.
- b. Vital signs will include pulse rate, respiratory rate, body temperature, and systolic and diastolic blood pressure (average of 3 readings will be taken in a resting state).
- c. Anterior and posterior segments ocular examination, including dilated ophthalmoscopy, IOP, and slit lamp biomicroscopy (see [Appendix 2](#)).
- d. Check central retinal artery perfusion following study injection.
- e. At Day 1: measure IOP at 10 (+/- 5) and 60 (+/- 10) minutes following the EYP-1901 dose/sham injection. If IOP measurements at any study time points are 30 mmHg or higher, two additional measurements should be performed and IOP recorded as a mean of three measurements.
- f. All CFP images will be assessed by the CRC to determine the ETDRS-DRSS scores.
- g. Spectral-domain – optical coherence tomography angiography (SD-OCTA) or swept-source – optical coherence tomography angiography (SS-OCTA) imaging to be collected at these time points at pre-specified study sites where SD-OCTA equipment is available.
- h. Clinical laboratory testing will include HbA1c, hematology, serum chemistry, coagulation, and urinalysis evaluations (refer to the study Laboratory Manual).
- i. Documented HbA1c test results dated 60 days prior to the Screening Visit will be accepted.
- j. Females of childbearing potential only. Positive urine pregnancy results will be confirmed by a serum pregnancy test.
- k. Pharmacokinetic analyses of vorolanib and X-297, its main metabolite, will be performed on blood plasma samples.

This document is confidential.

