## **10.2. Secondary Efficacy Endpoint Analyses**

### Response Endpoints

The analysis and summarization performed for the primary endpoint ([Section 10.1](#)) will be repeated for the following secondary efficacy endpoints.

- Percentage of subjects improving ≥2 steps from baseline in the DRSS score in the study eye at Weeks 24 and 48.
- Percentage of subjects improving ≥2 steps from baseline in the DRSS score in the study eye at each timepoint (remaining timepoints apart from Weeks 24, 36, and 48)
- Percentage of subjects worsening ≥2 steps from baseline in the DRSS score in the study eye at each timepoint
- Percentage of subjects improving ≥3 steps from baseline in the DRSS score in the study eye at each timepoint
- Percentage of subjects worsening ≥3 steps from baseline in the DRSS score in the study eye at each timepoint
- Percentage of subjects who developed a vision-threatening complication due to diabetic retinopathy in the study eye through Week 24, through Week 36, and through Week 48.

Vision threatening complications due to diabetic retinopathy will be indicated by the presence of “Vitreous hemorrhage” or the presence of “Tractional retinal detachment” reported on the Ocular Examination – Dilated Ophthalmoscopy CRF (proliferative diabetic retinopathy [PDR] events, and “Neovascularization for the Iris” answered as “Yes” or “Neovascularization for the Angle” answered as “Yes” per the Ocular Examination - Slit Lamp Biomicroscopy CRF (anterior segment neovascularization [ASNV] events).

Summarization and analyses will be repeated for the following subgroups – baseline DRSS in the study eye of 43 (moderate NPDR), 47 (moderately severe NPDR), and 53 (severe NPDR), and baseline DRSS score in the study eye, categorical ( $\leq 47$ ,  $\geq 53$ ).

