**This document is confidential.**

- Percentage of subjects who developed CI-DME in the study eye through Week 24, through Week 36, and through Week 48.

The occurrence of a CI-DME event in the study eye will be identified via examination of centrally read custom algorithm CST data and adverse events. For the CST data at any given time point, if results are available for no more than 2 raters, the average value will be used, and if results are available for three raters, the median value will be used. CI-DME will have occurred when an adverse event occurs which has a mapped preferred term of 'Cystoid macular oedema', 'Diabetic retinal oedema', or 'Macular oedema', for which the temporally closest CST measurement is greater than or equal to 320 microns.

Two additional endpoints will also be summarized.

- Macular edema (Definition 1) will have occurred when an adverse event occurs which has a mapped preferred term of 'Cystoid macular oedema', 'Diabetic retinal oedema', or 'Macular oedema'.
- Macular edema (Definition 2) will have occurred when an adverse event occurs which has a mapped preferred term of 'Cystoid macular oedema', 'Diabetic retinal oedema', or 'Macular oedema', and which has treatment with a concomitant medication with a mapped preferred term of 'aflibercept', 'ranibizumab', 'bevacizumab', or 'faricimab'.

- Percentage of subjects who received anti-VEGF or additional standard of care intervention due to ocular diabetic complications in the study eye through Week 24, through Week 36, and through Week 48.

Anti-VEGF use is identified in reported concomitant medication data as those medications with ATC code 'S01LA'.

Unique mapped concomitant medication and procedure terms and associated information will be reviewed by masked ophthalmology team members to identify those mapped concomitant medication and procedure terms that indicate the use of additional standard of care intervention due to ocular diabetic complications.

- Percentage of subjects who received PRP in the study eye, inclusive of subjects undergoing vitrectomy with endo-laser, through Week 24, through Week 36, and through Week 48.

Unique mapped procedure terms and associated information will be reviewed by masked ophthalmology team members to identify those mapped procedure terms that indicate receipt of PRP.

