#### Time to Event Endpoints

Time (in weeks) to develop any vision threatening complication (PDR/ASNV) in the study eye through a particular time point (Week 24, Week 36, or Week 48) will be computed as the earliest date of a vision threatening complication in the study eye prior to the particular time point minus the date of study drug administration, plus 1 day, divided by 7 days per week. For subjects not experiencing a vision threatening complication in the study eye prior to the particular time point of interest, the subject will be censored at their date of discontinuation from the study (if prior to the time point of interest) or at the time point of interest.

Time (in weeks) to develop a CI-DME in the study eye, macular edema in the study eye per Definition 1, and macular edema in the study eye per Definition 2 will be computed in a similar manner.

This document is confidential.

Each time to event endpoint will be summarized with the number and percentage of subjects who experienced the endpoint, number and percentage of subjects who were censored, and Kaplan-Meier estimates of median and first and third quartiles. The EYP-1901 treatment arms will be compared to the sham IVT group using a log-rank test. A corresponding Kaplan-Meier plot will be prepared for the FAS only.

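### Time to PDR/ASNV: event-free subjects are censored at study exit or at the time point, not at the last eye examination, so unexamined time counts as event-free (usually a small effect)

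*SAP*

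**What the plan says.** **Censoring.** Under Time to Event Endpoints in SAP 10.2, for a subject without a vision-threatening complication before Week 24, 36 or 48, "the subject will be censored at their date of discontinuation from the study (if prior to the time point of interest"), and otherwise at the time point of interest. The last examination is not mentioned, and neither document defines how the discontinuation date is set.

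**How PDR/ASNV events are found.** Under Response Endpoints in SAP 10.2, vitreous hemorrhage or tractional retinal detachment counts when "reported on the Ocular Examination – Dilated Ophthalmoscopy CRF". Neovascularization of the iris or angle counts "per the Ocular Examination - Slit Lamp Biomicroscopy CRF (anterior segment neovascularization [ASNV] events"). No other source is named.

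**When eyes are examined.** SAP 4.1: "Following study drug IVT injection on Day 1, subjects will return at Weeks 4, 12, 24, 36 and 48". For early leavers, SAP Table 1, footnote a: "Subjects who terminate the study prior to the Week 48 (end of study) visit should undergo all procedures noted for the early termination visit". That visit includes a bilateral ocular examination. Protocol 4.4 makes the return best effort: "the Investigator should make every effort to have the subject return to the clinic for the end of study safety evaluations".

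**Edema endpoints.** Time to CI-DME, macular edema per Definition 1 and "macular edema in the study eye per Definition 2 will be computed in a similar manner". Their events start from an adverse-event report: "CI-DME will have occurred when an adverse event occurs which has a mapped preferred term of" three listed edema terms, with the temporally closest central subfield thickness at or above 320 microns. Definition 1 needs the adverse event alone; Definition 2 adds anti-VEGF treatment.

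**Outputs.** SAP 10.2 plans counts of events and censored subjects, Kaplan-Meier median and quartiles, a log-rank test against sham, and a Kaplan-Meier plot for the FAS. The SAP's index of tables lists FAS and PP versions and no alternative censoring date.

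**The concern.** A PDR/ASNV event can enter the data only at an examination. Time after a subject's last examination cannot produce an event, yet both parts of the rule can count it as time at risk:

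- The discontinuation part does so when a subject leaves without an early termination examination and the recorded exit date is later than the last visit attended. Death and withdrawal of consent are among the termination categories in Protocol 4.4.
- The time-point part does so for a subject who is still enrolled but unexamined, or whose recorded exit falls after the time point.

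Scheduled visits after Week 12 are 12 weeks apart, so one missed visit can leave a long unexamined stretch. If other subjects' events are found during it, the denominators are too large and the curve shows too few events. With about 20 subjects per arm, two or three such subjects in one arm can visibly move that arm's curve. Prevention of worsening retinopathy is a stated secondary objective. The PP analysis does not test the rule for those who leave before Week 36, because the PP Set excludes them.

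**Working it through.** The documents give no event rate, dropout rate or expected event count for these endpoints, so there is no stated figure to reproduce. Every rate and count below is assumed, except the arm size (about 20, SAP 4.3) and the visit weeks (SAP 4.1).

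**Step 1. One arm, three censoring dates.** Assume 20 subjects, 2 events found at Week 24, 2 at Week 36, and 3 event-free subjects last examined at Week 12 who have no early termination examination. The Kaplan-Meier rate through Week 36 is 1 minus the product of (1 − events / number at risk).

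| Censoring of the 3 subjects | At risk, Week 24 | At risk, Week 36 | Survival | Rate |
|---|---|---|---|---|
| SAP rule, discontinued after Week 36 (censored at Week 36) | 20 | 18 | (18/20)(16/18) = 0.800 | 20.0% |
| SAP rule, discontinued at Week 30 | 20 | 15 | (18/20)(13/15) = 0.780 | 22.0% |
| Last examination, Week 12 | 17 | 15 | (15/17)(13/15) = 0.765 | 23.5% |

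The discontinuation part accounts for 23.5 − 22.0 = 1.5 points and the time-point part for 23.5 − 20.0 = 3.5 points. A discontinuation date before Week 24 would give 23.5%, the same as last-examination censoring, because no event falls in the gap.

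**Step 2. Range at a single event visit.** With 1 to 4 such leavers and 1, 2 or 4 events at one visit in an arm of 20:

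- Smallest difference (1 leaver, 1 event): 1/19 − 1/20 = 5.3% − 5.0% = 0.3 points.
- Largest difference (4 leavers, 4 events): 4/16 − 4/20 = 25.0% − 20.0% = 5.0 points.

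**Step 3. Simulation.** Events were detectable only at examinations (Weeks 4, 12, 24, 36, 48 and any early termination visit). The first two rows assume no early termination examinations and a recorded exit 12 weeks after actual departure.

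| Assumption | SAP rule | Last examination |
|---|---|---|
| True 48-week rate 20%, dropout 20% | 18.7% | 19.7% |
| True 48-week rate 40%, dropout 20% | 38.2% | 39.8% |
| Every leaver has an early termination examination, or exit is recorded without lag | practically the same | practically the same |

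At a true rate of 10%, the same lag and no early termination examinations, the gap was about 0.1 to 0.5 points over dropout of 5% to 20%.

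**Step 4. Log-rank test.** The Step 1 arm is compared with an arm of 20 with complete follow-up to Week 36.

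| Events in comparator | p, SAP rule, exit after Week 36 | p, last examination |
|---|---|---|
| 0 | 0.037 | 0.023 |
| 1 (Week 24) | 0.16 | 0.11 |
| 2 (Weeks 24 and 36) | 0.38 | 0.27 |

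The p-value moves but does not cross 0.05 in any of the three cases. In simulation under no treatment difference, with dropout of 20% or 40% against 5%, rejection was 4.6% to 5.3% under the SAP rule and 4.6% to 5.1% with last-examination censoring.

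**Step 5. Planned quartiles.** In Step 1 survival stays above 0.75 under all three dates, so neither the first quartile nor the median is reached. The tabulated event counts and quartiles are the same; only the curve and the log-rank test change.

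**The case against.** **The rule rarely matters.** All early leavers are asked to attend a visit with an ocular examination, and when they attend on the exit date the two dates coincide. Three subjects in 20 leaving without it is a heavy assumption. The endpoints are secondary, the study is not powered, and no landmark Kaplan-Meier rate is planned. All of this stands and limits the size. It does not remove the mismatch between how events are found and how follow-up is counted.

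**The edema endpoints.** A reader might infer that CI-DME follow-up should stop at the last SD-OCT, since the definition uses a thickness. The documents do not support this. The trigger is an adverse-event report, which may be spontaneous (Protocol 7.1.6) and is collected until study completion (Protocol 7.1.7). The closest thickness reading may precede the report, so an event can still count after the last scan. Censoring event-free subjects at the last SD-OCT would give events a longer window than non-events. For these endpoints study exit is close to a defensible date.

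**Bias between arms.** A reader might also infer that sham is made to look safer, or that the log-rank result is materially distorted. The documents do not say which arm would lose unexamined subjects, and Step 4 shows little effect on the test. If subjects leave because they feel worse, that is informative dropout, which last-examination censoring does not cure.

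**Conclusion.** The point holds for time to PDR/ASNV as a low-cost improvement of modest consequence. Both parts of the rule can count unexamined time as event-free, and the resulting bias in the Kaplan-Meier curve is downward. Under the assumptions shown, the illustrative arm differs by 1.5 or 3.5 points, depending on which part applies; the simulated gap reaches about 1.7 points and the extreme hand example 5.0. Any effect requires subjects without an examination at exit or at the time point, a censoring date later than their last examination, and other subjects' events recorded in between. A claim that all four time-to-event endpoints share the flaw, or that the treatment comparison is unreliable because of it, goes further than the documents allow.

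**What to change.** In SAP 10.2, Time to Event Endpoints, replace the censoring sentence with two rules:

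- **PDR/ASNV:** censor event-free subjects at the last study-eye dilated ophthalmoscopy and slit-lamp examination on or before the time point, including early termination and unscheduled examinations. Keep the current rule as a sensitivity analysis.
- **CI-DME and macular edema Definitions 1 and 2:** censor event-free subjects at the last adverse-event assessment or contact on or before the time point, not at the last SD-OCT.

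The cost is a short text change, one derived date per endpoint type from data already collected, and one extra run for the sensitivity analysis. The downside is slightly less follow-up time and smaller numbers at risk. Informative dropout would need separate treatment.

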#### Area Under the Curve Endpoint

Observed BCVA values, change from baseline to each follow-up visit, and area under the curve (AUC) for change from baseline in BCVA through Week 24, Week 36, and Week 48 will be summarized descriptively. AUC through each time point of interest will be computed using the trapezoidal rule normalized to months, with a final unit of letters. Mean AUC for change from baseline in BCVA through Week 24, Week 36, and Week 48 will be compared between each active treatment arm and sham IVT using analysis of covariance (ANCOVA) with treatment arm as the main effect and baseline BCVA as a covariate. A plot of mean change from baseline in BCVA score over time will be prepared for the FAS.

#### Change from Baseline in DRSS Step

DRSS scores (not including indeterminate results) will be coded to numeric values for change in step analysis as indicated in Table 6.

**Table 6: Mapping of DRSS Scores to Numeric Steps**

DRSS Score	Coded Numeric Step
10	0
20	1
35	2
43	3
47	4
53	5
61	6
65	7
71	8
75	9
85	10

The coded numeric values represent whole steps on the DRSS, where Step 0 is no diabetic retinopathy and Step 10 is advanced proliferative diabetic retinopathy. Baseline is defined as the last non-missing DRSS measurement prior to the initiation of study treatment. Change from baseline is computed as follow-up step minus baseline step; a negative change indicates improvement in disease and a positive change indicates worsening of disease.

Observed values and change from baseline will be summarized descriptively by treatment group for the full analysis set.

The SAS MIXED procedure (MMRM) will be used with the REPEATED statement for visits with an unstructured covariance structure and a RANDOM statement set at the subject level. The model will include change from baseline at each visit as the dependent variable and fixed effects for treatment and visit and the interaction between treatment and visit, and baseline DRSS step as a covariate. The Kenward-Roger approximation will be used to estimate denominator degrees of freedom. If there is a convergence issue (lack of convergence in general, or convergence with a non-positive definite estimated

This document is confidential.

G-matrix or non-positive definite Hessian matrix) with the unstructured covariance structure, a Toeplitz or Autoregressive (1) [AR(1)] covariance structure will be used, following this sequence, until convergence is achieved. If the model still does not converge, no results will be reported. Model-based point estimates (i.e., least squares means and least squares mean differences, 80%, 85%, 90%, 95%, and 97.5% CI, and p-values) will be reported at each visit.

This document is confidential.

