### 10.1. Primary Efficacy Endpoint Analysis

The primary efficacy endpoint is the percentage of subjects improving  $\geq 2$  steps from baseline in the DRSS score at Week 36 in the study eye. The percentage of subjects improving  $\geq 2$  steps from baseline in the DRSS score will be summarized descriptively using counts and percentages of subjects by randomized treatment arm at each scheduled visit (Weeks 4, 12, 24, 36, and 48) and the corresponding 95% Clopper-Pearson CI will be presented for each treatment group. PPD

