14.2.16.2 Summary of Change from Baseline in Diabetic Retinopathy Severity Scale (DRSS) Step in the Study Eye at Each Follow-up Visit – Mixed Effect Model for Repeated Measures (MMRM) (Full Analysis Set)

14.2.17 Percentage of Subjects With  $\geq 2$ -step Improvement From Screening in Diabetic Retinopathy Severity Scale (DRSS) Score in the Study Eye at Each Follow-up Visit (Full Analysis Set)

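### The MMRM for change in DRSS step adds a subject-level random effect to an unstructured visit covariance, so the first-choice model fails the SAP's own convergence rule by construction

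*SAP*

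**What the plan says.** SAP Section 10.2, under the heading on change from baseline in DRSS step, fits PROC MIXED with a "REPEATED statement for visits with an unstructured covariance structure and a RANDOM statement set at the subject level". The mean model has "fixed effects for treatment and visit and the interaction between treatment and visit, and baseline DRSS step as a covariate". On inference it says: "The Kenward-Roger approximation will be used to estimate denominator degrees of freedom".

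A convergence issue is defined as "lack of convergence in general, or convergence with a non-positive definite estimated" "G-matrix or non-positive definite Hessian matrix) with the unstructured covariance structure, a Toeplitz or Autoregressive (1) [AR(1)] covariance structure will be used", in that order. The last step is: "If the model still does not converge, no results will be reported".

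The test on the estimated G matrix shows that a random effect is really intended; RANDOM is not just loose wording for the subject identifier. The SAP does not say whether that effect is an intercept, a slope or both. It does not say whether Toeplitz is the homogeneous or the heterogeneous form. Nothing elsewhere removes the RANDOM statement or makes it conditional.

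The results go to Table 14.2.16.2, listed in SAP Section 18 as "Mixed Effect Model for Repeated Measures (MMRM) (Full Analysis Set"). They comprise least squares means and differences, confidence intervals at five levels, and p-values at each visit.

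**The concern.** An unstructured covariance over visits can already represent any within-subject covariance, including whatever a random intercept or slope would contribute. With both in one model, the data cannot divide the total covariance between the G side and the R side.

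The redundancy alone would not damage the treatment estimates, because the total covariance remains estimable. The harm comes through the convergence rule. It treats the symptoms of redundancy as failure and moves to a more restrictive structure, so a sequence meant for occasional trouble with the data is set off by the specification itself.

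Two things are at stake. The covariance behind the reported intervals and p-values would not be the pre-specified first choice. Which covariance replaces it would turn on matters the SAP leaves open.

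**Working it through.** The SAP states no figure for this model, so there is none to reproduce. The check is algebra, supported by a numerical example.

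**Inputs.** Visits: SAP Section 10.1 summarises DRSS "at each scheduled visit (Weeks 4, 12, 24, 36, and 48"), so T = 5. Sample: about 60 subjects, about 20 per arm (SAP Section 4.3). Mean parameters: 3 arms × 5 visits + 1 baseline covariate = 16.

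**Step 1: parameters against rank.** The marginal covariance is V = ZGZ′ + R. A 5 × 5 symmetric V has 5 × 6 / 2 = 15 distinct elements, so no structure can have rank above 15. Rank here is that of the derivative of those elements with respect to the covariance parameters.

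| R structure | Random effect | Parameters | Rank |
|---|---|---|---|
| Unstructured | none | 15 | 15 |
| Unstructured | intercept | 16 | 15 |
| Unstructured | slope | 16 | 15 |
| Unstructured | intercept and slope | 18 | 15 |
| Toeplitz, homogeneous | none | 5 | 5 |
| Toeplitz, homogeneous | intercept | 6 | 5 |
| Toeplitz, homogeneous | slope | 6 | 6 |
| Toeplitz, heterogeneous | intercept | 10 | 10 |
| AR(1) | none | 2 | 2 |
| AR(1) | intercept | 3 | 3 |

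The first choice is over-parameterised whichever random term is meant.

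**Step 2: why this meets the SAP's failure definition.** Take a random intercept with variance s. Replacing R by R − cJ and s by s + c, where J is the matrix of ones, leaves V and the likelihood unchanged while R stays positive definite. If the fit stops at s > 0, the likelihood is flat in that direction and the Hessian is singular. If it stops at s = 0, G is not positive definite. With intercept and slope together, G may instead be non-zero but rank-deficient, which is also not positive definite.

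**Step 3: numerical confirmation.** One data set was simulated with 60 subjects, the 16 mean parameters and integer step changes. The assumptions were random-intercept variance 0.36, residual variance 0.5, AR correlation 0.5 and about 10% dropout.

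- −2 REML log-likelihood is 127.100587 at random-intercept variances 0, 0.095, 0.190 and 0.343. R is positive definite at each; the admissible range is 0 to 0.381.
- The smallest Hessian eigenvalue is 2.5 × 10⁻¹⁴ with the random intercept and 11.1 without it.
- For homogeneous Toeplitz with a random intercept it is 4 × 10⁻¹³, against 6.7 without.

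A second simulated data set of the same size behaved the same way. −2 REML log-likelihood was 167.165 at variances 0, 0.115, 0.230, 0.346 and 0.438. The Week 36 difference (0.0466) and its standard error (0.2604) were identical at all five.

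**Step 4: where the sequence ends.** Suppose RANDOM is an intercept, Toeplitz is homogeneous and the same triggers apply at that step. Toeplitz then also fails (rank 5 of 6), leaving AR(1) plus intercept or no model result. With a random slope only, or with heterogeneous Toeplitz plus intercept, the sequence stops at Toeplitz.

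**Step 5: what a one-variance fallback could cost.** Assume SDs of change of 0.8, 0.9, 1.0, 1.1 and 1.2 at Weeks 4, 12, 24, 36 and 48, with complete data and a normal approximation. The pooled SD is √[(0.64 + 0.81 + 1.00 + 1.21 + 1.44)/5] = √1.02 = 1.010. Coverage is 2Φ(1.96 × 1.010/SD) − 1, and width relative to correct is 1.010/SD.

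| Week | SD | Coverage of nominal 95% CI | Relative width |
|---|---|---|---|
| 4 | 0.8 | 98.7% | 1.26 |
| 12 | 0.9 | 97.2% | 1.12 |
| 24 | 1.0 | 95.2% | 1.01 |
| 36 | 1.1 | 92.8% | 0.92 |
| 48 | 1.2 | 90.1% | 0.84 |

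These figures apply to any fallback with one common variance, homogeneous Toeplitz as well as AR(1) plus intercept.

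**The case against.** The strongest case accepts the algebra and disputes the consequence.

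- **Scope.** Change in DRSS step is not among the secondary endpoints in SAP Section 5.2. The study is not powered for testing (SAP Section 4.3), and Protocol Section 11.3.7 calls all analysis descriptive. This stands and limits the weight of the point. The table will still carry p-values and intervals at five levels, so its model should be one that can be fitted as written.
- **Estimates are intact.** The redundancy alone leaves the difference and its model-based standard error unchanged, and the fallbacks are pre-specified. The first part is true. The second does not help, because the fallback is reached by construction and displaces a structure the data could support.
- **The path to AR(1) is conditional.** Read literally, the G and Hessian triggers attach to the unstructured fit, and later steps need only converge. On that reading homogeneous Toeplitz plus intercept could be reported. This is fair, and AR(1) should not be called inevitable. It also shows that the text does not determine the model.
- **The coverage loss is hypothetical.** The SDs are assumed, and the loss is zero if the SD is constant. The same loss would remain under the proposed fix if the unstructured model failed for ordinary reasons. Both points stand: the figures show what losing the unstructured covariance could cost, not a prediction.
- **Software and timing.** SAS was not run, and rounding could decide which warning appears, or whether any does. SAP Section 13 has outputs produced and approved masked before the unmasked run, so a failure would probably surface then. That is a good time to correct the text, but it does not correct it.

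**Conclusion.** The concern holds. The first-choice covariance is not identifiable under any reading of the unnamed random term (rank 15 with 16 or 18 parameters), and the SAP's own rule rejects every solution it can produce. This rests on algebra with five visits and needs no assumption about the data. How SAS would report the failure was not tested.

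The practical size is limited and partly unknown. Only Table 14.2.16.2 is affected. The primary responder summary with its Clopper-Pearson intervals and the descriptive summary of step change are not. If a one-variance fallback is used and the spread of change grows over time, late intervals are too narrow and early ones too wide. Under the assumed SDs, Week 36 coverage falls 95 − 92.8 = 2.2 percentage points short and Week 48 coverage 95 − 90.1 = 4.9 points short. It should be fixed, but it does not threaten the trial's main result.

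**What to change.** Delete the RANDOM statement from the model description, and with it the G-matrix trigger. Keep the REPEATED statement for visit within subject with an unstructured covariance, the Kenward-Roger degrees of freedom, the Hessian and general non-convergence triggers, and the existing Toeplitz then AR(1) order. Without RANDOM, all three structures are identifiable (15 of 15, 5 of 5 and 2 of 2), and the unstructured fit reaches the same maximised likelihood as the over-parameterised one.

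Heterogeneous versions of the fallbacks would also protect against unequal variances if the unstructured fit fails for ordinary reasons. They are optional and not part of this correction.

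The cost is a few words in the SAP and one line of code, with no change to any endpoint or data set. It should be made before the Week 36 unmasking, so that the covariance is not chosen with treatment results in view.
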